5. RESEARCH INTERVENTION PLAN

5.1 Administration Schedule

Ad/PSA

All patients will receive three injections of 0.16 ml. (0.125 ml. vaccine + 0.035 ml. Gelfoam) of the Ad/PSA subcutaneously in the right thigh unless patient condition precludes the use of that leg, in which case the left thigh will be used for all three injections. The dose of the vaccine, based upon our results from the Phase I trial, will be 1 x 108 pfu (4.4 x 109 particles) in the Gelfoam matrix. The Gelfoam comes in sterile patient-ready packages. The virus will be suspended in sterile saline and the Gelfoam powder added in a ratio of 30 mg of powder per ml. of virus suspension. Injections will be spaced apart by 30 days, such that each patient will receive the vaccine on days 1, 30, and 60. The use of the matrix has been shown in collaborative pre-clinical experiments to enhance infection of host cells by the virus. Results from the Phase I trial indicated that the injection of the vaccine in Gelfoam did not produce any adverse events greater than those produced by the vaccine in an aqueous suspension. The vaccine induced anti-PSA immune response in patients injected as an aqueous or Gelfoam vaccination. Injections will be carried out in the University of Iowa Clinical Research Unit (CRU). Each subject will be required to stay in the CRU for two hours and observed for early signs of toxicities.

5.2 5.2 Design and Stages

The ideal design would be a two-stage design of Simon (1989) requiring 32 patients. But due to the complexity of the trial, a more conservative approach consisting of using 32 patients in a one-stage design at efficacy level and a two looks at toxicity level as means of stopping rules will be carried out. By using a one-stage design at efficacy endpoint, we are making the probability of early termination for efficacy purposes to be zero. The reason for this design is due to the nature of the research intervention as outlined in section 10. Stopping design based on toxicity is as follow: one look after 17 subjects are treated and another look after 25 subjects are treated. If 5 out of 17 show vaccine-related grade 3 toxicity or higher, the trial will stop. Otherwise, an additional 8 subjects will enter the trial. If 7 out of 25 show grade 3 toxicity or higher, the trial will stop otherwise we will proceed to full registration of 32 patients to assess efficacy.

6. Adverse Events

Toxicity will be graded according to the NCI common toxicity criteria "Common Terminology Criteria for Adverse Events" (NCI-CTCAE v3.0 can be accessed at website: http://ctep.cancer.gov/forms/CTCAE Index.pdf). Non-hematologic and Hematologic dose limiting toxicity (DLT) will be defined as described in Section 8.5.1.

6.1 Definitions

Adverse Event (AE) is any untoward medical occurrence in a patient or clinical investigation subject administered a pharmaceutical product and that does not necessarily have a causal relationship with this research intervention. An AE can therefore be any unfavorable and unintended sign (including an abnormal laboratory finding), symptom, or disease temporally associated with the use of a medicinal (investigational) product, whether or not related to the medicinal (investigational) product.

This will also include intercurrent diseases and accidents observed during the research intervention period as well as corresponding events during drug-free, pre- and post-intervention periods, under placebo or in a reference group receiving drug or non-drug therapy.

Serious adverse event (SAE) is any untoward medical occurrence that:

- a. results in death
- b. is life-threatening^B
- c. requires inpatient hospitalization or prolongation of existing hospitalization
- d. results in persistent or significant disability or incapacity
- e. is a congenital anomaly / birth defect or
- f. is another medically important condition.^C

^B The term "life-threatening" in the definition of "serious" refers to an event in which the patient is at risk of death at the time of the event; it does not refer to an event, which hypothetically might have caused death if it were more severe.

^c Medically important conditions that may not result in death, be life-threatening or require hospitalization may be considered as SAE when, based upon appropriate medical judgment, they may jeopardize the patient or may require intervention to prevent one of the outcomes listed in the definition above. Examples of such events are intensive treatment in an emergency room or at home for allergic

6.2 Procedures of documentation of AEs

All AEs occurring during the study must be documented, regardless of the assumption of a causal relationship, on the respective AE CRF. All events which occurred after signed informed consent should be documented. The investigator should ensure that all events are recorded that occurred within at least 4 weeks after the last exposure to the study drug (through Day 90).

Documentation of AEs includes: date of onset and offset, intensity, frequency, seriousness, related interventions and outcome. The investigator will also evaluate the probability of a causal relationship of the adverse event to the study medication as being: "definite, probable, possible, unlikely, or unrelated."

All unanticipated problems involving risk to subjects or others, serious adverse events related to participation in the study and subject deaths related to participation in the study will be promptly reported bν [contact]),bν email ([contact]), or by [contact]) to the USAMRMC, Office of Research Protections, Human Research Protection Office. A complete written report will follow the initial notification. In addition to the methods above, the complete report will be sent to the U.S. Army Medical Research and Materiel Command, ATTN: MCMR-ZB-PH, [name].

The medical monitor is required to review all unanticipated problems involving risk to volunteers or others, serious adverse events, and all volunteer deaths associated with the protocol and provide an unbiased written report of the event. At a minimum, the medical monitor should comment on the outcomes of the event or problem, and in the case of a serious adverse event or death, comment on the relationship to participation in the study. The medical monitor should also indicate whether he/she concurs with the details of the report provided by the study investigator. Reports for events determined by either the investigator or medical monitor to be possibly or definitely related to participation and reports of events resulting in death should be promptly forwarded to the HSRRB.

Expedited reporting

The investigator must immediately report serious adverse events (SAE) occurring or observed during the course of the study and within 4 weeks of last administration of the study drug to the FDA, IRB, OBA, and CRU.

The order of reporting of SAEs is the following: reported to the Principal Investigator within 24 hours of the event; the PI will then report the event to the FDA, OBA, Institutional Biosafety Committee (IBC), and DOD within 7 days of the event and to the IRB within 10 days of the event. After notifying the proper agencies by telephone of an SAE the "Serious Adverse Event Report "must also be sent by fax to the agencies whether or not complete information is available at the time. If complete information is unavailable the investigator must provide follow-up information to the agencies as soon as it is known.

bronchospasm; blood dyscrasias or convulsions that do not result in hospitalization; or development of drug dependency or drug abuse. N.B.: The term "severe" is often used to describe the intensity (severity) of an event (such as: mild, moderate, or severe e.g., pain). The event itself may be of relatively minor medical significance (such as severe headache). This is not the same as "serious", which is based on patient/event outcome or action criteria usually associated with events that pose a threat to patient's life or vital functions. Seriousness (not severity) serves as a guide for defining regulatory reporting obligations.

In particular, the investigator must inform the agencies and committees by phone and fax using the timeline described above of occurrence of immediately life-threatening SAEs or SAEs with fatal outcome. SAEs must be reported to the site's IRB according to the IRB's requirements.

Important: The investigator must report any SAE to the FDA, IRB, OBA, and CRU, regardless of causality.

Reports will be evaluated by the Medical Monitor/Sponsor. FDA/HPB and investigators will be informed as required by the regulations. The same information will also be made available to all participating investigators as well as to other investigators participating in different clinical trials utilizing the same study medication.

It should be noted that, although the Ad/PSA vaccine contains the gene for PSA, there is no need for patients to utilize contraceptive practices. The adenovirus will not be transmitted from patient to his partner.

7 MEASUREMENT OF CLINICAL AND IMMUNOLOGICAL EFFICACY

7.1 Methods of Malignant Disease Evaluation - Each patient will have a baseline evaluation prior to the injection of the Ad/PSA vaccine. The measurements will include physical exam, temperature, weight, serum PSA, blood chemistries, urinalysis, a quantitative bone scan for bone metastases, chest x-ray, and CT for soft tissue metastases, and performance status for quality of life.

Patients will be seen in the Urology and Oncology Clinics (see Table 6 for schedule). The injection site will be examined for evidence of erythema, induration and necrosis and patients will have their temperature and weight recorded and the patients will be interviewed to determine whether they experienced any adverse reactions. Blood samples will also be taken for standard laboratory testing and measurement of PSA and anti-PSA immune responses (see Table 6). Patients recruited from the DMMCC will return to that facility for their follow-up examinations and laboratory testing on days 44, 74, and at 6, 9, 12 months and all subsequent visits. At the 6 month, 9 month, 12 month, and subsequent semi-annual visits each patient will be evaluated comparing the baseline visit measurements to those obtained at the specific visit.

Because changes to the clinical status of the patients will be prolonged, continued follow up will be important. Therefore, patients will return to the clinic for two additional visits, at 18 and 24 months, unless travel distance is a prohibitive factor. Follow-up of patients for survival will occur every 6 months by telephone.

- 7.2 Scans Bone scans will be performed at 90 days, 6 months, and 12 months during the first year as well as the 24 month visit and annually until progression. If there is measurable disease by CT scan at registration then CT scans will also be performed using the same schedule as the bone scans.
- 7.3 Use of Serum PSA for Disease Evaluation Based upon our pre-clinical experiments and the results from the Phase I clinical trial we expect the immunized men to produce anti-PSA antibodies. The levels of antibody will be measured by a flow cytometry assay as described by Cavacini, et al. used in our Phase I clinical trial (40). We will also explore the use of a second serum marker for prostate cancer, hK2 in collaboration with [name], [name], and [name] at the Mayo Clinic. Investigators at Mayo, along

with Hybritech, Inc. have been exploring hK2 and published a number of papers in recent years on the subject (67-70). Patient sera from each clinic visit will be sent to Mayo where they will measure the levels of hK2. We will use the data to evaluate the effect of anti-PSA antibodies on both PSA and hK2 in the sera of vaccinated patients.

PSA measurements, CT and bone scans are routinely used to follow disease recurrence and/or progression in individual prostate cancer patients and as such would be considered standard of care. Laboratory measurements such as hematology, liver function and kidney function chemistries, while are routinely used to follow the health of a prostate cancer patient, would not normally be performed at the frequency proposed in this trial to assess possible vaccination toxicities. Therefore, they would be considered part of the research protocol.

7.4 Experimental Evaluation of the Ad/PSA Vaccination

- 7.4.1 Blood will be collected prior to each injection of the Ad/PSA vaccine and at return dates indicated in Table 6, page 26. Two separate samples will be collected; one in red top tubes to allow collection of serum from coagulated blood and a second in heparinized tubes to permit collection of lymphocytes.
- 7.4.2 Levels of PSA, hK2, anti-PSA antibodies, and anti-adenovirus antibodies will be measured in the serum.
- 7.4.3 Anti-PSA T cell immune responses will be measured by ELISPOT analysis using the methods developed for, and used in, our Phase I clinical trial. In addition to measuring the anti-PSA T cell activity, we will also measure anti-adenovirus T cell activity as well as reactivity to stimulation with cytomegalovirus (CMV). A nonspecific stimulus will be provided by PMA and ionomycin for each patient's lymphocytes.

7.5 Definitions of Response –

7.5.1 Primary Endpoint - PSA doubling-time response

- 7.5.1.1 Definition: a 50% increase in the PSADT compared to pre-enrollment PSADT.
- 7.5.1.2 PSADT will be calculated based on the MSKCC calculator, available at http://www.mskcc.org/mskcc/html/10088.cfm.
- 7.5.1.3 PSADT response will be measured at 9 and 18 months after initiation of the research intervention.
- 7.5.1.4 Three measurements of PSA, spaced at least 2 weeks apart, will be required prior to study enrollment. Post-intervention PSADT will be based on PSA levels at 3, 6 and 9 months (9 month PSADT calculation) and 3, 6, 9,12,15,18 month levels (18 month PSADT calculation).

7.5.2 Secondary Endpoint – PSA response

7.5.2.1 Definition: a 50% reduction in the pre-research intervention PSA value, verified with a second measurement >28 days later.

7.5.3 Progression:

Progression of disease is defined for 3 different categories of disease: measurable lesions; non-measurable/non-target lesions; and PSA-only disease. The first category of disease to progress will meet the definition of progression in this trial, as follows:

7.5.3.1 Progression for measurable disease:

Definition: Measurable lesions are defined as those that can be accurately measured in at least one dimension (longest diameter to be recorded) and is equal or greater than 20 mm with conventional techniques (CT, MRI, x-ray) or equal or greater than 10 mm with spiral CT scan. All tumor measurements must be recorded in millimeters (or decimal fractions of centimeters)

All measurable lesions (up to a maximum of 10) representative of all involved organs should be identified as target lesions and will be recorded and measured at baseline. Target lesions should be selected on the basis of their size (lesions with the longest diameter) and their suitability for accurate repetitive measurements (either by imaging techniques or clinically). A sum of the longest diameter (LD) for all target lesions will be calculated and reported as the baseline sum LD. The baseline sum LD will be used as reference to further characterize the objective tumor response of the measurable dimension of the disease.

All other lesions, including non-measurable small lesions as defined above and bone metastasis, will be identified as non-target lesions (see definition of progression for non-target lesions below).

Progression is defined if any of the criteria below are met:

- at least a 20% increase in the sum of the LDs of target lesions (taking as a reference the smallest sum LD recorded since the treatment started) or the appearance of two or more new lesions
- development of an indication for radiation therapy while on treatment
- 7.5.3.2 Progression for non-measurable disease/non-target lesions:

Non-measurable disease/non-target lesions: progression of disease is defined as any of the following:

- 7.5.3.2.1 worsening bone scan as evidenced by the appearance of more than two new lesions, not felt to be consistent with a tumor flare; worsening of pre-existing lesions (increase in intensity or size of a lesion) may be difficult to interpret and in such a case will not be considered the evidence of progressive disease; or
- 7.5.3.2.2 appearance of new metastatic lesions outside the bone; or unequivocal progression of existing non-target lesions. Because a clear progression

- of non-target lesions only is exceptional, such circumstances should be discussed with the study co-investigator's; or
- 7.5.3.2.3 development of an indication for radiation therapy while on treatment
- 7.5.3.3 Progression for patients with PSA-only disease

PSA progression will be evaluated as follows:

- 7.5.3.3.1 In patients that had any PSA decline from baseline:
 - 7.5.3.3.1.1 increasing PSA by 25% above the nadir plus
 - 7.5.3.3.1.2 an increase in PSA by a minimum of 2 ng/ml from the nadir plus
 - 7.5.3.3.1.3 confirmation by second consecutive rising PSA >28 days later
- 7.5.3.3.2 in patients whose PSA has not declined, progression is defined as
 - 7.5.3.3.2.1 an increase in PSA by 25% above the pretreatment level plus
 - 7.5.3.3.2.2 an increasing PSA by a minimum of 2 ng/ml relative to the study entry PSA value, plus
 - 7.5.3.3.2.3 confirmation by second consecutive rising PSA >28 days later.
- 7.5.4 Onset of Response In patients that present with radiologic evidence of metastases onset of response is the onset of PR or CR. For patients with biochemical disease only the onset of response is defined by the first drop in serum PSA.
- 7.5.5 Duration of Response In patients that present with radiologic evidence of metastases, duration of response is time from onset of PR or CR, whichever occurs first, (even if the patient later has a CR) until objective evidence of progression. In patients with PSA-only disease, duration of response is time from first drop in serum to objective evidence of progression. Progression is defined in Section 7.5.3, beginning on page 20.
- 7.6 Timing of Toxicity Assessments Toxicity assessment will occur as stated in the calendar.

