The effects of vaccination on serum PSA and on patient survival were also evaluated as a secondary endpoint in the phase I trial. Although there was no sustained decline in individual PSA levels, the PSA doubling times (PSADT, calculated based on 3 pre-enrollment consecutive PSA

measurements) were reduced in 54 percent of the patients compared to pre-vaccine administration, with the best responses occurring in patients immunized with the highest dose of the vaccine (Table 4). In addition, published survival nomograms for patients with hormone refractory prostate cancer were applied to patients in this phase I trial (40,41). Table 5 shows that 57% of all patients at all doses, whether injected with the vaccine as an aqueous suspension or in the collagen matrix, had a survival time longer than that predicted by the nomogram, The range of increased survivals in the different groups was 33% to 100%.

Table 4
PSA Doubling Time (DT) in Phase I Patients

Vaccine Dose & Vehicle	Percent iNcreased PSA DT					
100	2004					
10 ⁶ aqueous	33%					
10 ⁶ matrix	33%					
10 ⁷ aqueous	67%					
10 ⁷ matrix	67%					
10 ⁸ aqueous	25%					
10 ⁸ matrix	62%					
Total	54%					

Table 5
Ad/PSA Phase I Trial
Predicted and Actual Patient Survival

Vaccine Dose	Vehicle	Percent with Longer Than Predicted Survival
10 ⁶	Aqueous	33%
10 ⁶	Matrix	67%
10 ⁷	Aqueous	100%
10 ⁷	Matrix	33%
10 ⁸	Aqueous	56%
10 ⁸	Matrix	50%
Overall		57%

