3. SELECTION OF PATIENTS

As described in Section 1.6 prostate cancer patients with hormone refractory metastatic disease will be enrolled in the study.

3.1 Inclusion criteria:

- 3.1.1 Men with prostate cancer who present with evidence of hormone refractory disease (D3).
- 3.1.2 Men with a positive bone scan or a positive CT scan (with obvious soft tissue metastasis or lymph nodes >1 cm), a PSA doubling time of ≥6 months, and a total PSA of <10 ng/ml, and asymptomatic OR men with a negative bone scan and a negative CT scan with any PSA doubling time and asymptomatic.
 - 3.1.3 Scans must be obtained within 6 weeks of initiation of treatment.
 - 3.1.4 Written informed consent.
 - 3.1.5 Age > 18 years.
 - 3.1.6 Required laboratory values (obtained within 2 weeks of initiation of treatment)
 - 3.1.6.1 Serum creatinine < 2.0 mg/dL
 - 3.1.6.3 Adequate hematologic function: granulocytes \geq 1800 per mm³, platelets \geq 100,000 per mm³, WBC >3700, and lymphocytes >590.
 - 3.1.6.4 Adequate hepatocellular function: AST <3x ULN and total bilirubin <1.5 mg/dl (unless bilirubin elevation is consistent with Gilbert's syndrome).

- 3.1.6.5 Castrate levels of testosterone of ≤50 ng/ml.
- 3.1.7 PSA used as an eligibility criterion must be drawn within 28 days prior to injection number 1 and will be redrawn on Day 1 for use as a baseline value.
- 3.2 Exclusion criteria:
 - 3.2.1 Active or unresolved clinically significant infection.
 - 3.2.2 Parenteral antibiotics <7 days prior to initiation of treatment.
 - 3.2.3 Evidence of prior or current CNS metastases. Specific imaging is not necessary in the absence of signs or symptoms.
 - 3.2.4 Co-morbid medical conditions which would result in a life expectancy (participation) of less than 1 year.
 - 3.2.5 Patients with compromised immune systems; congenital, acquired, or drug-induced (immunosuppressive agents) will be excluded from the study. Use of prednisone at doses higher than 10 mg daily (or equipotent steroid doses) for more than 7 days within 3 months of initiation of treatment is not allowed.
 - 3.2.6 Pre-existing malignancies that required treatment within the past 5 years except for basal or squamous cell cancers of the skin.
 - 3.2.8 Prior participation in any vaccine studies for non-infectious diseases.

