- 4.5 No patient may be enrolled or begin research intervention prior to registration and assignment of a patient number. As a follow-up, University of Iowa Cancer Center will provide the investigator with written confirmation of each patient's registration.
- 4.6 All investigators will be notified by the Chair of the Protocol Review and Monitoring Committee or by the trial's Data and Safety Monitoring Board if the study is placed on administrative hold, and when the study is completed or closed to further patient enrollment.
- 4.7 Patients must begin the vaccine protocol within 30 days of registration (date the study committee approves patient eligibility).

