	Std. of Care or Res.	Prior to Reg. ¹	Day 1 First Inj.	30 d. 2 nd Inj.	44 d.	60 d. 3 rd Inj.	74 d.	90 d.	6 mo	9 mo	12 mo	18 mo.	24 mo.	Annual to prog.	Follow- up ⁷
Immunization ²	R		X	X		X									
Physical Examination	S		X	X		X		X							
Adverse Event Assessments	R		X	X		X		X							
Performance Status	S		Х	Х		X		X	X	X	Х				
Vital Signs	S		X	X		X		Χ	X	X	Х				
Weight	S		Х	Х		X		Χ	Х	Х	Х				
Blood for PSA & PAP ³	S/R		Х	X (R)		X(R)		Χ	Х	Х	Х	Х	Х		
anti-PSA Ab, and lymphocytes for cellular immunity	R	Х	Х	Х	Х	Х	Х	Х	X _e	X ⁶	X ₆	Х	Х		
CBC, differential	R	Х		Х		X		Х	Х	Х	Х	Х	Х		
AST, ALT, LDH, alkaline phosphatase, bilirubin	R	Х		Х		Х		Х							
Creatinine	R	Х		Х		X		Х							
Urinalysis	R	Х		Х		X		Х							
Serum testosterone	R	Х													
Chest x-ray	R	Х		X ⁴		X ⁴		X ⁴							
Bone scan	S	Х						Х	Х		Х		Х	Х	
Abdominal/pelvic CT	S	Х							X ⁵		X ⁵				
Survival assessment	R														X ⁷

S = Procedures considered "Standard of Care" for prostate cancer patients.

R = Procedures considered "Research" as part of this Clinical Trial.

In the event of holidays or other extenuating circumstances the times on the table may vary by ± 4 days for the first 90 days. Beyond that every effort will be made to see the patient within 2 weeks of the expected date of return, but the investigator is willing to allow for other arrangements for the convenience of the patient.

¹ Reg. = Registration, the date patient eligibility approved by the study team.

² Androgen deprivation therapy must continue for the duration of study participation.

³ If the PSA meets the definition of progression, partial or complete response, confirm the PSA results >/= 28 days.

⁴ will be repeated only if abnormal at screening or if patient develops a fever.

⁵ will be repeated only if abnormal at screening.

⁶ to be performed even if there is disease progression (up to 12 months from study entry) if the patient has consented to this in the informed consent (question in section "How long will I be on the study?)."

⁷ Follow-up for survival every 6 months by telephone.

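### The untreated Day 1 PSA enters neither doubling time as written; adding it to the baseline tightens the baseline slope at no extra draw, by an amount that depends on spacing the protocol leaves open

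*Combined protocol and SAP*

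**What the plan says.** Section 7.5.1.1 defines a response as "a 50% increase in the PSADT compared to pre-enrollment PSADT". For the baseline, section 7.5.1.4 states: "Three measurements of PSA, spaced at least 2 weeks apart, will be required prior to study enrollment". It then lists the post-intervention values: months 3, 6 and 9 for the 9-month calculation, and months 3 to 18 for the 18-month calculation. Day 1 is not on that list.

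Section 3.1.7 says that the eligibility PSA "must be drawn within 28 days prior to injection number 1" and that PSA "will be redrawn on Day 1 for use as a baseline value". Section 7.4.1 confirms that the Day 1 sample is untreated: "Blood will be collected prior to each injection of the Ad/PSA vaccine". In Table 6 the row "Blood for PSA & PAP" is marked for Day 1 and has no mark in the column before registration.

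On the order of events, section 4.5 says: "No patient may be enrolled or begin research intervention prior to registration and assignment of a patient number". Section 4.7 allows up to 30 days from registration to the first injection.

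Section 1.4 shows where the baseline definition comes from. The Phase I PSADT was "calculated based on 3 pre-enrollment consecutive PSA" measurements.

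**The concern.** The baseline slope is one of the two quantities in the primary comparison. Three values may lie as little as two weeks apart, so that slope can rest on a 28-day window and one residual degree of freedom. A noisy baseline makes more men look like responders by chance and hides some true responders. Both errors count against fixed response rates in section 10 (30% unacceptable, 50% hoped for).

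Against that background, the plan already collects a fourth untreated PSA in every treated man, later than the other three, and the wording gives it no place in either slope. A later point lengthens the window, which is where a slope gains most precision.

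**Working it through.** The plan states no PSA variance, no standard error and no PSADT precision, so there is no figure of its own to reproduce.

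**Does Day 1 belong to either slope?**
- Baseline: 7.5.1.1 and 7.5.1.4 speak of values before enrollment. Under 4.5 and 4.7, registration comes first and the injection follows, so Day 1 is not a pre-enrollment value.
- Post-intervention: the list in 7.5.1.4 starts at month 3.
- So, as worded, Day 1 is in neither.

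**Precision of the baseline slope**

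Assumptions: PSADT comes from an ordinary least-squares slope of log PSA on time (the protocol points to an external calculator and gives no formula), errors are independent with equal variance, Day 1 is time 0, and the last of the three values is the eligibility PSA, so it lies at most 28 days before Day 1.

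SE(slope) = σ/√Sxx, where Sxx is the sum of squared deviations of the sampling days from their mean. If d is the distance from the mean of the three earlier days to Day 1, adding Day 1 gives

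Sxx(4) = Sxx(3) + 0.75 d²

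and the cut in standard error is 1 − √(Sxx(3)/Sxx(4)). The noise σ cancels. With equal spacing s and gap g to Day 1, Sxx(3) = 2s² and d = s + g.

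| Days of the three PSAs | Sxx, three values | Sxx with Day 1 | Cut in SE |
|---|---|---|---|
| -56, -42, -28 | 392 | 1,715 | 52% |
| -42, -28, -14 | 392 | 980 | 37% |
| -90, -60, -28 | 1,923 | 4,563 | 35% |
| -118, -73, -28 | 4,050 | 8,047 | 29% |
| -35, -21, -7 | 392 | 723 | 26% |
| -194, -104, -14 | 16,200 | 24,312 | 18% |
| -208, -28, -14 | 23,411 | 28,619 | 10% |

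Example, first row: s = 14 and g = 28, so d = 42, Sxx(4) = 392 + 0.75 × 1,764 = 1,715, and 1 − √(392/1,715) = 0.52.

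With equal spacing the floor is reached as g approaches 0: 1 − √(2/2.75) = 14.7%. The top, 52%, needs the minimum spacing together with the longest gap. Unequal layouts can fall below the floor, as the last row shows. Residual degrees of freedom rise from 1 to 2 in every layout.

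**Which half of the comparison is weaker?** Taking months 3, 6 and 9 as days 90, 180 and 270, the post-intervention Sxx is 2 × 90² = 16,200. At 2-week spacing the baseline SE is √(16,200/392) = 6.4 times the post-intervention SE. At 90-day spacing the two are equal.

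**Effect on chance responders**

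Further assumptions, none from the documents: true PSADT constant at 6 months, lognormal PSA noise with the stated coefficient of variation (CV), post values at days 90, 182 and 274. A man counts as a responder if his baseline slope is positive and either his post slope is zero or negative or his baseline slope is at least 1.5 times his post slope. Simulated share of responders with no vaccine effect:

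| Layout | CV | Without Day 1 | With Day 1 |
|---|---|---|---|
| -56, -42, -28 | 10% | 36% | 24% |
| -56, -42, -28 | 15% | 40% | 32% |
| -56, -42, -28 | 20% | 43% | 36% |
| -194, -104, -14 | 10% | 8.6% | 7.5% |

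For -208, -28, -14 the change is about half a point. Detection of a true doubling of PSADT rises by 2 to 7 points in the first four layouts of the precision table, and by about 1 point for -194, -104, -14.

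**The case against.** Several points on the other side are fair.

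- **No express exclusion.** Section 7.5.1.4 says what is required before enrollment, which can be read as a minimum. A reader might infer that the protocol rules Day 1 out, or contradicts itself by calling Day 1 a baseline value. It does neither. Day 1 can serve as the reference level for PSA response (7.5.2) and PSA progression (7.5.3.3), and a reference level is not a slope. What stands is that the wording leaves Day 1 out of the slope. On the minimum-of-three reading, two analysts could compute different endpoints for the same man, so the text would still need fixing.
- **Precedent.** Phase I used three pre-enrollment values, and keeping that definition preserves comparability. This explains the wording but is no reason to leave out an untreated value already in hand.
- **Selected layouts.** A reader who tries only layouts with a long gap to Day 1 might infer a cut of roughly 30% to 50% as a general figure. The protocol fixes neither a maximum spacing nor a minimum gap, and permitted layouts go down to about 10%.
- **The main cause lies elsewhere.** The high chance-response rates come from allowing a short baseline window. At the 2-week minimum with a 28-day gap, 32% and 36% chance responders remain at CV 15% and 20% even with Day 1. This is correct: adding Day 1 is not a cure.
- **Table 6.** A reader might infer from the empty cell before registration that no earlier PSA is taken. Sections 3.1.7 and 7.5.1.4 require those values in text, so the missing mark is clerical.

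**Conclusion.** The point holds as a cheap improvement to the primary endpoint. As worded, an untreated PSA drawn in every man is in neither doubling time, and adding it always makes the baseline slope more precise.

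The size is not a single number. Under a log-linear least-squares slope with independent, equal-variance errors, the cut in standard error is about 15% to 52% with equal spacing and about 10% in some unequal layouts. It matters most when sites use values near the 2-week minimum: in the illustration at CV 10%, chance responders move from above the 30% reference rate to below it. It matters little when the three values span many months. The chance-responder percentages also rest on the assumed PSADT, noise level and handling of flat or falling PSA, and only the 9-month calculation was simulated, not the 18-month one.

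**What to change.** In sections 7.5.1.1 and 7.5.1.4, define the baseline PSADT for response as the slope through all qualifying pre-enrollment PSAs plus the Day 1 pre-injection PSA. State that the eligibility test in section 3.1.2 uses the pre-enrollment values alone. As a clerical matter, mark the eligibility PSA of section 3.1.7 in the pre-registration column of Table 6.

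The cost is protocol wording, with no extra blood draw. There are two small downsides: each man then has two baseline PSADTs, one for eligibility and one for response, and the response definition departs from the Phase I one. Reporting the three-value version as a sensitivity analysis would keep the link to Phase I. If the noise of a short baseline window is to be dealt with as well, the protocol would also need a minimum span for the pre-enrollment values.
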